10. STATISTICAL CONSIDERATIONS

This section describes the statistical analyses and associated procedures intended to be performed during the analysis of the data collected during this clinical study. A detailed description of the statistical analyses will be provided in the statistical analysis plan.

The key elements of the statistical analysis plan are summarized in Table 10-1. A comprehensive description is provided in Section 10.4.

Table 10-1 Summary of Statistical Analysis Plan

Study Design Overview	This is a prospective, randomized, double-blind, placebo-controlled, multicenter, two-arm, parallel-group Phase 3 study comparing the efficacy and safety of xevinapant versus matched placebo, when administered in combination with platinum-based standard fractionation IMRT in previously untreated LA-SCCHN patients suitable for definitive CRT.
Treatment Assignment	Eligible participants will be randomized in a 1:1 ratio to receive xevinapant + CRT (Arm A) or matched placebo + CRT (Arm B) using dynamic allocation with complete randomization. Stratification factors are described in Section 6.3.
Analysis Sets	The following analysis sets will be used for planned analyses: Intent-to-treat, Safety, analysis set. Please refer to Section 10.3 for the description of the analysis sets.
Primary Endpoint/Hypothesis	Xevinapant prolongs EFS as assessed by the BIRC in previously untreated patients with LA-SCCHN suitable to receive CRT compared to matched placebo when administered in combination with platinum-based standard fractionation IMRT.
Statistical Methods for Key Efficacy Analyses	The hypothesis on EFS will be evaluated by comparing xevinapant to placebo in combination with CRT using a stratified log-rank test. The stratification factors are tumor size (T4 vs other) and lymph node involvement (N0-1 vs N2 vs N3). The hazard ratio will be estimated using a Cox-proportional hazard regression model adjusted for randomization stratification factors. Treatment effect on other time-to-event endpoints will be estimated using Cox regression model adjusted for randomization stratification factors. Estimation of the treatment effect on binary endpoints will be done using a logistic model adjusted for randomization stratification factors. Please refer to Section 10.4.2 and Section 10.4.3 for the detailed description of the efficacy analyses.
Statistical Methods for Key Safety Analysis	Only descriptive statistics will be provided for safety endpoints. Please refer to Section 10.4.4.
CCI	

Abbreviations: BIRC: Blinded Independent Review Committee; CRT: chemoradiotherapy; EFS: event-free survival; IDMC, Independent Data Monitoring Committee; IMRT, intensity-modulated radiotherapy; LA-SCCHN: locally advanced squamous cell carcinoma of the head and neck; OS: overall survival; PA: primary analysis.

10.1. Statistical Hypotheses

10.1.1. Primary Hypothesis

Xevinapant prolongs EFS as assessed by the BIRC in previously untreated LA-SCCHN patients compared to matched placebo when administered in combination with platinum-based standard fractionation IMRT.

10.1.2. Secondary Efficacy Hypothesis

Secondary efficacy testing will be done with a hierarchical procedure for the following secondary endpoint. It is hypothesized that:

Xevinapant + CRT prolongs OS compared to placebo + CRT.

[figure not shown]
Other efficacy endpoints will be analyzed without any type I error adjustment.

10.2. Sample Size Determination

Sample size calculation and evaluation of robustness was perform using R version 3.6.1 and R package 'rpact' version 2.0.4. as well as EAST 6.5.1.

10.2.1. Sample Size

The sample size was calculated considering the primary endpoint (blinded independent-assessed EFS) and interim analyses.

It is anticipated that 700 participants will be randomized overall (~1000 participants screened).

Note: After global recruitment reaches the planned sample size for the ITT population (n=700), a Chinese extension cohort will be opened to reach randomization of approximately 106 Chinese participants from China Mainland (see Section 13.9 for further details).

CCI		
		_

Justification of the assumptions:

[figure not shown]
Following the review of the literature (Table 10-2) and considering the variations in populations, treatment regimen-dose modulations, endpoint definitions and natural variation, it is expected that the Placebo + CRT group (Arm B) will experience a median time to EFS of about 17 months, leading to an exponential parameter λ of 0.041.

Table 10-2 Published studies used for the sample size assumptions

Reference	Population	Number of participants	Regimen	mPFS (months)
	Locally advanced	155	TPF-CCRT	14.6
(Hitt et al. 2014)	inoperable	156	PF-CCRT	14.3
	·	128	CCRT	13.8
Nonmetastatic, histologically prover stage III or IV (Posner et al. squamous cell		255	TPF CCRT	15
carcinoma of the oral cavity, larynx, oropharynx, or hypopharynx	246	PF CCRT	10	
(Bonner et al.	LA-SCCHN, stage III or IV; including HPV	211	Cetuximab-RT	17.1
2006)	positive OPC	213	RT	12.5
(Geoffrois et al.	Patients with bulky nodal spread—N2b	179	Carboplatin+5FU + RT	12.5
2018)	or N2c to N3	151	TPF+cetuximab+RT	11.5
(Tao et al. 2018)	Patients with N0-2b, non-operated, stage III or IV (nonmetastatic) LA-SCCHN (including oral cavity, HPV-positive OPC)	204	CT-cetuximab-RT	37.9
		201	Cetuximab-RT	22.4

Abbreviations: 5FU: 5-fluorouracil; **CT**: chemotherapy; **HPV:** Human Papilloma Virus; **LA-SCCHN**: Locally Advanced Squamous Cell Carcinoma of the Head and Neck; **mPFS:** median progression-free survival; **OPC:** Oropharyngeal cancer; **PF-CCRT:** cisplatin and 5-fluorouracil -concurrent chemoradiation; **RT:** radiotherapy; **TPF-CCRT:** docetaxel (Taxotere), cisplatin and 5-fluorouracil - concurrent chemoradiation.

The Debio 1143-201 Part B Phase 2 study showed promising results (PFS improvement corresponding to a HR=0.37). These results together with a literature review were used to determine the EFS treatment effect assumptions. Thus, we expect that the addition of xevinapant to CRT will lead to a treatment effect color, corresponding to a difference of at least color in the prolongation of median EFS in the xevinapant + CRT group (Arm A) (median time estimate and exponential parameter colors) as compared with Placebo + CRT group. This improvement in outcome is considered clinically relevant and is consistent with published data (Bonner et al. 2006); (Blanchard et al. 2011).

10.2.2. Robustness of Sample Size

10.2.2.1. Robustness of Sample Size for Event-free Survival

Table 10-3 presents the expected power according to alternative hazard ratios while interim and primary analyses are triggered using assumptions from Section 10.2.1. In a situation where the hazard ratio is smaller than expected, the power at the first interim analysis provides good characteristics. In a situation where the hazard ratio is larger than expected, the power is at an appropriate level at primary analysis.

10.2.2.2. Robustness of sample size for overall survival

Table 10-4 presents the number of events, expected timing of analyses and the power according to alternative hazard ratios (expected median OS in control at column and annual lost to follow-up/dropout rate for OS at col.).

10.2.3. Sample Size for PK

PK blood samples will be collected from all randomized participants, ensuring sufficient collection of PK data to perform PK analyses and subsequent exposure/response analyses.

10.3. Analysis Populations

The following analysis sets will be used for the planned analysis of the global study population:

Intent-to-treat (ITT): The ITT set will include all randomized participants. Participants will be analyzed according to the randomized treatment assignment following the intention-to-treat principle. The ITT set will be the primary set for all efficacy and HRQL variables.

Safety (SAF): The SAF set will include all participants who received at least one dose of study medication. Participants will be analyzed according to the actual treatment received. The SAF will be used for all safety analyses.

Pharmacokinetics (PK): The PK set will include all the participants who have undergone at least one PK sample scheduled. The PK set will be used for all PK analyses.

10.4. Statistical Analyses

10.4.1. General Approach

Time-to-event data will be summarized based on Kaplan-Meier estimates, including but not limited to frequency and percentage at risk/censored, median, 1st and 3rd quartile, rate at predefined timepoints. Other continuous data will be described using descriptive statistics, including but not limited to the number of non-missing values (n), mean, standard deviation, median, minimum and maximum value. Categorical data will be described using the participant count and percentage in each category (including one for missing data).

Unless otherwise specified, all inferential tests will be one-sided. Type I error for primary objective null hypothesis is preserved at 0.025 one-sided using a group sequential design (O'Brien & Fleming type α spending).

Primary and selected secondary efficacy objectives will be evaluated in a hierarchical fixed sequence testing procedure (also called fixed sequence statistical strategy tests). Tests on the endpoints will be done in the predefined order specified in Section 10.1.2, all at the same significance level α , moving to the subsequent endpoint only after a success on the previous endpoint. Such a test procedure will preserve the overall type I error at 0.025 one-sided.

10.4.2. Analysis of the Primary Efficacy Endpoint

This section describes the statistical methods for the analysis of the primary endpoint.

The primary endpoint is EFS as assessed by the BIRC. Please refer to Section 3 for the definition of the primary endpoint and Section 11.2.4 for information on the BIRC. Supportive analysis will be done on EFS as assessed by Investigator.

Censoring rules for the primary and sensitivity analyses of EFS are described in Table 10-5. If a participant is meeting a multiple censoring situation, the earliest censoring criterion will be applied.

Primary treatment failure is defined as requirement of radical salvage surgery **before achieving a CR** that includes the primary tumor site, with documented viable tumor presenting anatomopathological findings even in the absence of formal RECIST v1.1 radiological progression, **occurring up to EOT visit**.

In the situation of a primary treatment failure, a participant will be considered to have an event (EFS) at the date of randomization (Michiels et al. 2009). This event can only occur during the treatment period. This rule aims to correct for potential bias in the follow-up schedules for tumor assessment during treatment (Michiels et al. 2009).

Table 10-5 Censoring rules for EFS

Situation	Primary	Sensitivity #1	Sensitivity #2
No evaluable baseline or post- baseline assessment*	Right censored at the date of randomization	Right censored at the date of randomization	Right censored at the date of randomization
Death, PD or any event entering in the definition of EFS after 2 or more	Right censored at last adequate assessment before the consecutive	Right censored at last adequate assessment before the consecutive	Not applicable

Situation	Primary	Sensitivity #1	Sensitivity #2
consecutive missing or inadequate tumor assessments	missing/inadequate assessments	missing/inadequate assessments	
Initiation of a new anticancer treatment for the disease under investigation before any event entering in the definition of EFS	Right censored at their last adequate assessment before the initiation of the new anticancer treatment	Not applicable	Not applicable
No death, PD, nor any event entering in the definition of EFS	Right censored at the date of their last adequate assessment	Right censored at the date of their last adequate assessment	Right censored at the date of their last adequate assessment

Abbreviations: EFS: Event-free survival; PD: Progressive disease

The Kaplan-Meier method will be used to estimate the EFS curve in each treatment group, see Section 10.4.1. Summary statistics, not limited to median, 1st and 3rd quartile, rate at 9, 12, 18, 24, 30 and 36 months after randomization, will be extracted from the Kaplan-Meier estimates.

The primary efficacy analysis will assess the difference in EFS between treatment arms using a one-sided stratified log-rank test at the α level of 0.025. The stratification factors are tumor size (T4 vs other) and lymph node involvement (N0-1 vs N2 vs N3). These factors were chosen among the randomization factors to avoid issues caused by very small sample stratum sizes. A Coxproportional hazard regression model adjusted for the randomization factors will be used on the EFS with primary censoring rule to derive the hazard ratio and 95% CI between the 2 randomized regimens. Ties will be handled by replacing the proportional hazards model by the discrete logistic model. The stratification factors used for the randomization of participants will be inserted as covariates in the regression model. EFS with sensitivity censoring rules will be analyzed with the same approach.

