1.2. Study Diagram and Flow

Figure 1-1 Study diagram

Abbreviations: D: day; EFS follow-up: Event-Free Survival follow-up; OS follow-up: Overall Survival follow-up

Figure 1-2 Study Flow

SCREENING

From Day -28 to Day 1 of Cycle 1 (up to 28 days)

Previously untreated patients with histologically confirmed LA-SCCHN (stage III, IVA or IVB as per AJCC/TNM) of the oropharynx, hypopharynx, or larynx, and suitable for definitive chemoradiotherapy

OPC tumors must be known to be HPV-negative (determined by p16 expression using IHC)

RANDOMIZATION 1:1 Xevinapant : Placebo From Day -7 to Day 1 of Cycle 1

Stratification by region (North America vs. Western EU vs. Rest of the World), primary tumor site (larynx vs. other), lymph node involvement (N0-1 vs. N2 vs. N3) and stage (T4 vs. other)

ARM A: Xevinapant + chemotherapy + IMRT

Combination Therapy: Cycles 1-3

Xevinapant, 200 mg/day, Days 1-14 Q3W cycles + concomitant IMRT, from Day 1 for 7 weeks (70 Gy in 35 fractions over 7 weeks, 2.0 Gy/fraction, 5 days/7)

+ cisplatin high dose (100 mg/m²), Day 2 Q3W cycles (or carboplatin at equivalent dose at C2 and/or C3 if the patient cannot receive cisplatin)

Monotherapy: Cycles 4-6 Xevinapant, 200 mg/day, Days 1-14 Q3W cycles

ARM B: Placebo + chemotherapy + IMRT

Combination Therapy: Cycles 1-3

Placebo, Days 1-14 Q3W cycles + concomitant IMRT, from Day 1 for 7 weeks (70 Gy in 35 fractions over 7 weeks, 2.0 Gy/fraction, 5 days/7)

+ cisplatin high dose (100 mg/m²), Day 2 Q3W cycles (or carboplatin at equivalent dose at C2 and/or C3 if the patient cannot receive cisplatin)

Monotherapy: Cycles 4-6
Placebo, Days 1-14 Q3W cycles

EOT

15 days (±7 days) after last study treatment administration (i.e, Xevinapant/placebo, chemotherapy or IMRT whichever is administered last):

clinical and radiological evaluation; HRQL

EFS FOLLOW-UP (data collection of EFS starts from randomization date)

•Day 1 of Month 7 (±2 weeks): clinical and radiological evaluation; HRQL

•Day 1 of Month 9 (±2 weeks): clinical and radiological evaluation

•From Day 2 of Month 9 to Day 1 of Month 30 : clinical and radiological evaluation every 3 months (±2 weeks); HRQL, CCI and ECOG PS evaluation yearly (±2 weeks)

•Day 1 of Month 33 (±2 weeks): clinical and radiological evaluation

•Day 1 of Month 36 (±2 weeks): clinical and radiological evaluation; HRQL, and ECOG PS

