8.2.2 Clinical Assessment	Decision tree for the determination of tumor status added (Figure 8-1).	To help investigators with clinical assessment when histopathology results or other clinical data are not consistent with the radiology report.	9.0
10.1.2 Secondary Efficacy Hypothesis	Update of the secondary endpoints to be used for the hierarchical testing procedure.	To focus on OS only, as OS is the most reliable endpoint regarding clinical benefit and	9.0

Section # and Name	Description of Change	Brief Rationale	Version Implemented
		complements the primary endpoint EFS	
10.2.1 Sample Size Determination 10.2.2 Robustness of Sample Size 10.4.7 Planned Analysis	Non-binding futility analysis for the primary endpoint EFS added.	To provide guidance for the IDMC via a futility boundary for the primary endpoint EFS at the interim analysis.	9.0
	Testing strategy for the secondary endpoint OS was specified.	To specify the OS testing strategy regarding effect size, control of the type I error, power, number of events.	
10.4. Statistical Analyses	Cox Model: Method how to handle ties was updated.	In case of a high number of ties, which is the case in the situation of predefined scan intervals, a more appropriate method how to handle ties is replacing the proportional hazards model by the discrete logistic model.	9.0
10.4.4.1 Adverse Events	Definition of TEAE.	Time period was specified for clarity.	9.0
13.5 Response Evaluation Criteria in Solid Tumors (RECIST) V1.1 applied to this study in locally advanced SCCHN	RECIST v1.1 revised by adding guidance on assessment for LA SCCHN.	Revised for clarity.	9.0
13.9 Country-specific Amendment for China	Country-specific Amendment for China added (v8.1 CHN)	To allow for the collection and analysis of data from approximately 106 China Mainland participants to adequately represent the Chinese population.	9.0
Throughout document	Minor editorial and document formatting changes.	Minor, therefore changes have not been summarized.	9.0
Synopsis: Study Population and Sample Size Section 4.1: Study Design and Overview Section 5: Study Population Section 5.5: Strategies for Recruitment and Retention. Section 10.2.1: Sample Size	Added wording on the addition of a China-specific extension cohort.	An additional China-specific extension cohort is added to increase the sample size of the overall Chinese population to approximately 15% (106 subjects) of the global ITT population, to adequately represent the Chinese population.	8.1

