14.1 Primary Efficacy Endpoint: Event-free Survival (EFS)

Event-Free Survival (EFS) time is defined as the time (in months) from randomization to the first occurrence of any of the following events as assessed by the BIRC: death due to any cause, disease progression (radiological or clinical), primary treatment failure, relapse (radiological or clinical) or occurrence of a new cancer (see Table 1). Death as reported on the eCRF page "Death" will also be considered in the derivation of EFS time.

$$EFS = (date of EFS event - randomization date +1) / 30.4375$$

Censoring rules for the primary and sensitivity analyses of EFS are described in Table 4 below. The last adequate tumor assessment is defined as the last tumor assessment result that is not "Not evaluable" or "Not assessed". If a participant is meeting a multiple censoring situation, the earliest censoring criterion will be applied.

Table 4: Censoring rules for EFS

Situation	Primary	Sensitivity #1	Sensitivity #2
No evaluable baseline or post-baseline assessment*	Right censored at the date of randomization	Right censored at the date of randomization	Right censored at the date of randomization
Death, PD or any event entering in the definition of EFS after 2 or more consecutive missing or inadequate tumor assessments	Right censored at last adequate assessment before the consecutive missing/inadequate assessments	Right censored at last adequate assessment before the consecutive missing/inadequate assessments	Not applicable
Initiation of a new anticancer treatment for the disease under investigation before any event entering in the definition of EFS	Right censored at their last adequate assessment before the initiation of the new anticancer treatment	Not applicable	Not applicable
No death, PD, nor any event entering in the definition of EFS	Right censored at the date of their last adequate assessment	Right censored at the date of their last adequate assessment	Right censored at the date of their last adequate assessment

Abbreviations: EFS: Event-free survival; PD: Progressive disease

^{*}Any EFS event is considered as a post-baseline assessment.

Table 5: Estimand Attributes EFS

Objective	Estimand Attributes
Primary	

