-	Endpoint: EFS as assessed by the BIRC defined as the time from randomization to the first occurrence of any of the following events (occurring within two scheduled tumor assessments after last evaluable assessment or randomization): Death from any cause Progression: Radiological, assessed per RECIST v1.1 or Clinical, with or without RECIST v1.1- radiologically documented progression, assessed endoscopically Primary treatment failure before achieving a CR: requirement for radical salvage surgery that includes the primary tumor site, with documented viable tumor presenting anatomopathological findings even in the absence of formal RECIST v1.1 radiological progression. Any radiological or clinical relapse after achieving a CR (loco-regionally), including any event defined as locoregional treatment failure, even in the absence of formal radiological progressive disease confirmation: Requirement for radical salvage surgery that includes the primary tumor site, regardless of anatomopathological findings or Elective neck dissection or biopsy, with positive viable tumor cells on anatomopathological findings at 22 weeks or later after randomization. Second cancers unless anatomopathological findings exclude squamous histology Population: Patients with LA-SCCHN Stage III, IVA or IVB suitable for definitive CRT Treatment: xevinapant and CRT followed by xevinapant vs placebo and CRT followed by placebo Intercurrent Event Strategy: Death within two missing scheduled tumor assessments after last evaluable assessment or randomization will be considered as event (composite strategy) Discontinuation of treatment: The endpoint will be analyzed regardless of
	 whether or not treatment has been discontinued (treatment-policy strategy) Start of subsequent anticancer therapy will be analyzed according to hypothetical strategy, i.e., tumor assessments after start of subsequent anticancer therapy will not be considered for analysis Population-Level Summary: Hazard Ratio

Objective	Estimand Attributes
Supplementary #1 (CSP Sensitivity #1)	Endpoint: EFS as assessed by the BIRC defined as the time from randomization to the first occurrence of any of the events (occurring within two scheduled tumor assessments after last evaluable assessment or randomization).
	Population: Patients with LA-SCCHN Stage III, IVA or IVB suitable for definitive CRT
	Treatment: xevinapant and CRT followed by xevinapant vs placebo and CRT followed by placebo
	Intercurrent Event Strategy:

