14.1.1 Primary Analysis of the Primary Efficacy Endpoint EFS

The primary efficacy analysis will assess the difference in EFS between treatment arms using a one-sided stratified log-rank test. The significance boundaries are adjusted accordingly to control the family-wise error rate (FWER) at 2.5% one-sided (see also IAP Table 3). The stratification factors are tumor size (T4 vs other) and lymph node involvement (N0-1 vs N2 vs N3). These factors were chosen among the stratification factors for randomization to avoid issues caused by very small sample stratum sizes.

A Cox-proportional hazard regression model adjusted for the randomization factors will be used on the EFS with primary censoring rule (Table 4) to derive the hazard ratio and 95% CI between the 2 randomized regimens. In addition, a two-sided repeated CI (RCI) for the hazard ratio will be reported (Jennison and Turnbull, 2000), to account for the group sequential design in the confirmatory analyses (interim and primary analysis, as applicable). Ties will be handled by replacing the proportional hazards model by the discrete logistic model. The stratification factors used for the randomization of participants will be inserted as covariates in the regression model. EFS with sensitivity censoring rules will be analyzed with the same approach.

A further estimate of the hazard ratio (including 95% confidence interval) will be calculated based on the Cox proportional hazards model stratified by the stratification factors tumor size (T4 vs other) and lymph node involvement (N0-1 vs N2 vs N3). Each stratum will define separate

baseline hazard functions. Ties will be handled by replacing the proportional hazards model by the discrete logistic model.

The null and alternative hypotheses can be described in terms of hazard ratios as:

$$H_0^{EFS}$$
: $\lambda_{(xevinapant + CRT)} / \lambda_{(placebo + CRT)} \ge 1$ versus

$$H_1^{EFS}$$
: $\lambda_{(xevinapant + CRT)} / \lambda_{(placebo + CRT)} < 1$,

where $\lambda_{(xevinapant + CRT)}$, $\lambda_{(placebo + CRT)}$ represents the hazard of EFS for the (xevinapant + CRT) and the (placebo + CRT) group respectively.

The SAS code for the stratified log-rank test and the Cox-proportional hazard regression model is specified in Appendix 6

The proportional hazards assumption for the analysis of EFS will be examined using graphical methods by means of log-log-Survival plots (log(-log(S(t)))) vs log(time) by treatment arm, plots=(lls) in PROC LIFETEST.)

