Appendix 6 – Programming Specifications

Stratified log-rank test:

```
proc lifetest data= ADTTE;
   time AVAL * CNSR(1,2,3,4);
   strata T N / group= TRTPN test= (logrank) trend;
   ods output TrendTests= logrank;
run;

CNSR ≠ 0 if censored, 0 otherwise
AVAL = EFS time in months
Randomization stratification factors: T = Tumor size, N = Lymph node involvement
TRTPN = planned treatment
```

Cox-Regression:

```
proc phreq data= ADTTE;
  class REGION(ref='Western Europe') SITE(ref='Other') N(ref='N0-1')
        T(ref='Other') TRTP (ref='Placebo') /param=ref;
 model AVAL*CNSR(1,2,3,4) = TRTP REGION SITE N T / rl ties = discrete;
 hazardratio 'treatment' TRTP/ diff=ref;
 hazardratio 'region' REGION / diff=ref;
 hazardratio 'tumor site' SITE / diff=ref;
 hazardratio 'lymph node' N / diff=ref;
 hazardratio 'T size' T / diff=ref;
 ods output HazardRatios= HR;
run;
CNSR \neq 0 if censored, 0 otherwise
AVAL = EFS time in months
Randomization stratification factors:
REGION = Region, SITE = Tumor Site, T = Tumor size, N = Lymph node involvement
TRTP = planned treatment
```

[figure not shown]
Kaplan-Meier Estimates:

```
proc lifetest data=ADTTE timelist=9,12,18,24,30,36 outsurv=surv reduceout;
  time AVAL * CNSR(1,2,3,4);
  strata TRTPN;
  ods output Quartiles=quar;
  ods output ProductLimitEstimates=est;
run;

[figure not shown]
CNSR ≠ 0 if censored, 0 otherwise
AVAL = EFS time in months
TRTPN = planned treatment
```

[figure not shown]
Logistic regression model:

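### The EFS hazard ratio is estimated with the discrete logistic tie option, whose coefficient is a log odds ratio; the exaggeration is small, but the estimator does not match the stated summary measure

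*Protocol*

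**What the plan says.** Protocol 10.4.2 specifies a Cox model, adjusted for the randomization factors, which "will be used on the EFS with primary censoring rule to derive the hazard ratio and 95% CI between the 2 randomized regimens". Two sentences follow that pull apart: the figure is a hazard ratio, and "Ties will be handled by replacing the proportional hazards model by the discrete logistic model".

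SAP 14.1.1 repeats both and adds a repeated confidence interval for the hazard ratio. It also adds a second estimate: "A further estimate of the hazard ratio (including 95% confidence interval) will be calculated based on the Cox proportional hazards model stratified by" tumor size and nodal status, with the same tie rule. The code in SAP Appendix 6 is "model AVAL*CNSR(1,2,3,4) = TRTP REGION SITE N T / rl ties = discrete". The primary EFS estimand in SAP Table 5 has "Population-Level Summary: Hazard Ratio", and the hypotheses in SAP 14.1.1 are written as ratios of hazards.

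The tie sentence also appears for OS (Protocol 10.4.3.1) and time to subsequent systemic treatment (10.4.3.8). PFS and LRC inherit it by reference to the EFS methods. Neither document prespecifies an Efron, Breslow or exact estimate, or says that the coefficient is an odds ratio. The amendment history (Protocol 13.10, change made in version 9.0) gives the reason for the choice: "In case of a high number of ties, which is the case in the situation of predefined scan intervals".

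**The concern.** The discrete option is more than a numerical device for ties. It fits a different model, in which the treatment coefficient is a log odds ratio of failing at each recorded time, given survival to that time. EFS is a continuous time recorded in days, and the rest of the plan works on the hazard scale: the estimand, the hypotheses and the log-log plots for checking proportional hazards.

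The stated rationale works against the choice. With few ties the option is unnecessary. With many ties the odds ratio departs from the hazard ratio, always in the direction of a larger effect.

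At stake are the label and value of the reported EFS effect, its 95% CI and, as SAP 14.1.1 reads, the repeated CI.

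**Working it through.** **Inputs.** Control median EFS 17 months, 700 participants and 1:1 allocation (Protocol 10.2.1 and 5.5). Hazard ratio 0.73 and 429 EFS events, with interim analyses at 279 and 365 (SAP Section 6, Tables 2 and 3). Recruitment over 22 months (SAP Table 2) and 5% dropout per year (Protocol 5.5). Visit days and ±2-week follow-up windows (Protocol Tables 1-1 and 1-3). EFS dating: "EFS = (date of EFS event - randomization date +1) / 30.4375" (SAP 14.1), using the earliest actual scan date (SAP 9.12.2) without visit windowing (SAP 9.10).

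**Plan's own figures.** Lan-DeMets spending with O'Brien-Fleming-type boundaries at one-sided 0.025 gives z = 2.546, 2.213 and 2.049. With HR boundary = exp(−2z/√d), these become 0.737, 0.793 and 0.821 (p = 0.005, 0.013, 0.020). Simulated power at HR 0.73, with the futility bound applied, is 53.3% + 25.8% + 9.1%, total 88.2%. SAP Table 3 reproduces.

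**Closed form.** Let p0 and p1 be the probabilities of failing within an interval of length D whose failures all receive one date. With λ = ln2/17 = 0.0408 per month:

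p0 = 1 − exp(−λD), p1 = 1 − exp(−0.73λD), OR = [p1/(1−p1)] / [p0/(1−p0)].

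| Interval sharing one date | p0 | p1 | OR when the HR is 0.73 |
|---|---|---|---|
| 1 day | 0.00134 | 0.00098 | 0.7299 |
| 2 weeks | 0.01858 | 0.01360 | 0.7281 |
| 3 months | 0.11513 | 0.08542 | 0.7178 |
| 134 days from randomization | 0.16431 | 0.12282 | 0.7121 |
| 6 months | 0.21701 | 0.16355 | 0.7055 |

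For 3 months, for example: 0.08542/0.91458 = 0.0934, 0.11513/0.88487 = 0.1301, ratio 0.718. The direction is always the same, and the gap grows with the fraction of the risk set that is tied.

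**Simulation under the plan's dating.** There were 1,000 trials per scenario, cut at 429 events with true HR 0.73. Each was fitted with the discrete and Efron likelihoods, treatment only.

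| Dating of events | Discrete | Efron | Gap |
|---|---|---|---|
| Scans scattered ±14 days, 30% of events are dated deaths | 0.7331 | 0.7334 | 0.0003 |
| Same, 30% of non-death events before Day 134 dated at randomization | 0.7328 | 0.7332 | 0.0004 |
| Scans scattered ±14 days, no dated deaths, all events before Day 134 dated at randomization (about 100 ties) | 0.7290 | 0.7331 | 0.0041 |
| Every event on a nominal visit day | 0.7201 | 0.7332 | 0.0131 |

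In the last row the log difference is ln(0.7332) − ln(0.7201) = 0.018, against a standard deviation of log HR of about 0.095. A smaller run of 300 trials per scenario, with visits on nominal days and 30% dated deaths, gave 0.7234 against 0.7299. With no dated deaths, single-trial log differences reached 0.036.

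The gap is small with scattered dates even though ties are common. In the 300-trial run with ±14-day scatter and 30% deaths, 56% of events shared a date with another, but the busiest date averaged only 7 events, a small fraction of those at risk.

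**The case against.** The strongest reply is that the plan does not create heavy ties. SAP 9.10 rules out windowing, dates are actual scan dates, and visits may move by two weeks either way. On that footing the gap is in the fourth decimal. This stands, and it is why the point is minor.

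One block of ties does not depend on visit scatter. Protocol 10.4.2 dates every primary treatment failure at randomization. Pushed to the extreme, that rule moves the estimate by about 0.004.

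A second reply is that the choice is disclosed and coherent with the test: the score test of the stratified, treatment-only discrete model is the stratified log-rank test. That is true, but it justifies the test, which needs no tie option in the Cox fit. It does not turn the coefficient into a log hazard ratio. The main Cox model also enters four factors as covariates, whereas the test stratifies on two.

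A third reply is that Efron is also an approximation and could err towards 1. The simulations do not show this. In the 300-trial run with visits on nominal days, Efron averaged 0.730 against a true 0.73, with or without dated deaths.

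A reader might infer that the tie option could affect whether EFS crosses its boundary. The documents do not support that. The note under SAP Table 3 bases decisions on p-values and gives the hazard ratios for information only, and the p-value comes from the log-rank test.

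**Conclusion.** The mismatch is real: the plan names a hazard ratio and specifies an estimator of an odds ratio. Its effect on the EFS estimate is one-directional and small. It is under 0.001 in typical conditions, about 0.003 to 0.004 if all early failures are dated at randomization, and on average at most about 0.013 if all events fall on nominal visit days. Type I error, power and the log-rank decision do not change.

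Two further readings are tempting but do not hold. The China consistency rule (Protocol 13.9) compares two risk reductions obtained by the same method, so any distortion acts in the same direction on both and largely cancels. OS uses the same option, but deaths are dated individually, so the effect there should be negligible.

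The sizes rest on assumptions that the documents do not supply: the share of EFS events that are deaths (0% or 30%), the share of early failures dated at randomization (0%, 30% or 100%), uniform accrual, uniform scatter of visits, and exponential times. The four covariates of the planned model were left out of the fits. Severity: minor.

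**What to change.** Set TIES=EFRON (or TIES=EXACT, the continuous-time likelihood) in every PROC PHREG call that produces a reported hazard ratio. Apply this to the covariate-adjusted model, the stratified model, the 95% CIs and the repeated CI. Delete the discrete-logistic sentence from Protocol 10.4.2, 10.4.3.1 and 10.4.3.8 and from both places in SAP 14.1.1, and change the option in SAP Appendix 6. Leave the stratified log-rank test as it is.

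If the sponsor wants to keep the discrete fit because it matches the log-rank score test, label it an odds ratio and report it only as a sensitivity result beside the Efron hazard ratio.

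The cost is one SAS option and a few sentences. Power and alpha are unchanged, and the reported hazard ratio may be very slightly less favourable.
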